For between-group comparability, participant randomization will be stratified by investigative site and tau pathology (low-medium versus high). Assignment to treatment groups will be determined by a computer-generated random sequence using an IWRS. Randomization into 1 stratum may be discontinued at the discretion of the sponsor.

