9.2. Sample Size Determination

Approximately 1800 participants will be randomly assigned in the study. It is anticipated that approximately two-third of participants have low-medium tau and approximately one-third of participants have high tau pathology.

The powering and sample size determination of the trial is based on the low-medium tau pathology population. The assumptions for the power calculation were based on the results of the Study AACG data. The mean progression levels in the placebo and donanemab arms from the MMRM analysis on iADRS were -10.06 and -6.86 points (approximately 32% slowing) over 18 months, respectively, with a standard deviation of 11.06. The assumed discontinuation rate of AACI is 30%. Multiple longitudinal datasets were simulated, and the NCS model with 2 degrees of freedom was fit to each sample to determine the power. With a sample size of approximately 1000 randomized participants in the low-medium tau pathology population, the NCS model with 2 degrees of freedom provides greater than 95% power to achieve statistical significance at a 1-sided 0.025 level for the treatment difference relative to placebo, as measured by iADRS at Month 18. If both treatment arms are placebo-like with no efficacy, the type I error is 2.5%.

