The main Study SAP will be finalized prior to unblinding of all participants in the placebo-controlled phase. This section is a summary of the planned statistical analyses of the most important endpoints including primary and key secondary endpoints and a more technical and detailed description of the statistical analyses will be described in the SAPs.

Any change to the data analysis methods described in the protocol will require an amendment only if it changes a principal feature of the protocol. Any other change to the data analysis methods described in the protocol, and the justification for making the change, will be described in the Study SAP and the clinical study report. Additional exploratory analyses of the data will be conducted as deemed appropriate.

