9.4.3. Primary Endpoint(s)

The primary objective of this study is to test the hypothesis that IV infusion of donanemab will slow the cognitive and/or functional decline of AD as measured by iADRS score compared with placebo in the population of participants with intermediate tau pathology at baseline and the overall population.

A NCS analysis (Chambers and Hastie 1992) with 2 degrees of freedom (DF) will be used to assess the difference between treatment groups in iADRS score at Week 76. The NCS model provides a type of smoothing function to the data and can adequately estimate longitudinal trajectories under a variety of shapes (for example, linear and quadratic) for each treatment group. The degrees of freedom of the model can be prespecified to establish the level of smoothing of the data. The number and location of the “knots” is utilized to parse out different time periods where the data may transition from one shape to another to provide an adequate fit and the location of the knots will be provided in the SAP.

The iADRS score at baseline and at each of the postbaseline visits will be included in model as a dependent variable. Study visit will be treated as a continuous variable with values equal to weeks between baseline and postbaseline exam dates. The model will include these fixed effects: NCS basis expansion terms (2 terms), NCS basis expansion term-by-treatment interaction (2 terms), baseline age, concomitant AChEI and/or memantine use at baseline (yes/no), and potentially other covariates will be included in the model and specified in the Study SAP. An unstructured variance-covariance structure matrix will be used to adjust for intra-subject correlation. If the unstructured variance-covariance structure matrix results in a lack of convergence, the following structures will be used in sequence:

- Heterogeneous Toeplitz covariance structure
- Heterogeneous autoregressive order 1 covariance structure
- Heterogeneous compound symmetry covariance structure, and
- Compound symmetry covariance structure.

The primary time point for treatment comparison will be at Week 76.

The primary efficacy analysis may be modified to use an alternative statistical model based on interactions with regulatory agencies and/or internal decision making, and if modified, the model will be outlined in the Study SAP prior to unblinding of the placebo-controlled phase.

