As a sensitivity analysis, a Bayesian Disease Progression Model (DPM) on the iADRS will evaluate possible slowing of disease progression with treatment of donanemab relative to placebo. The primary purpose of the DPM is to estimate a quantity known as the disease progression ratio (DPR), which measures the proportion of disease progression in donanemab-treated participants relative to placebo-treated participants.

The MMRM analysis will also be assessed for the iADRS. The change from baseline score on the iADRS at each scheduled postbaseline visit (according to the SoA) during the treatment period will be the dependent variable. The model for the fixed effects will include the following terms: baseline score, pooled investigator, treatment, visit, treatment-by-visit interaction, baseline-by-visit interaction, concomitant AChEI and/or memantine use at baseline (yes/no), and age at baseline. Visit will be considered a categorical variable. The null hypothesis is that the contrast between the donanemab group versus placebo at the last visit equals 0. An unstructured covariance matrix will be used to model the within-subject variance-covariance errors. If the unstructured covariance structure matrix results in a lack of convergence, the following tests will be used in sequence:

- heterogeneous Toeplitz covariance structure
- heterogeneous autoregressive covariance structure
- heterogeneous compound symmetry covariance structure
- compound symmetry covariance structure

The Kenward-Roger approximation will be used to estimate the denominator degrees of freedom.

The primary time point for treatment comparison will be at Week 76. The treatment group contrast in least-squares mean progression and its associated p-value and 95% CI will be calculated for the treatment comparison of donanemab versus placebo using the MMRM model specified above.

All analyses as described above, including the NCS with 2 DF, DPM, and MMRM models on iADRS will be assessed in the intermediate tau population and overall population.

Details about these analyses, as well as other sensitivity analyses including NCS with 3 degree of freedom, and quadratic models will be described in the SAP.

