9.4.4. Secondary Endpoint(s)

Similar to the primary endpoint of iADRS, each of the secondary efficacy outcomes will be assessed using NCS with 2 DF, DPM, and MMRM analyses for the intermediate tau population and overall population. These secondary efficacy outcomes include ADAS-Cog₁₃, ADCS-iADL, CDR-SB, and MMSE.

Longitudinal changes from baseline in amyloid plaque (as measured by florbetapir F18 PET scan) will be analyzed using MMRM including the following terms in the model: baseline biomarker value, treatment, visit, treatment-by-visit interaction, and baseline-by-visit interaction.

The change from baseline to endpoint in tau deposition (as measured by flortaucipir PET scan) will be analyzed using an analysis of covariance (ANCOVA) model with terms of baseline value and treatment. Atrophy in vMRI parameters will be analyzed using MMRM including the following terms in the model: treatment, visit, treatment-by-visit interaction, baseline vMRI, intracranial volume, and age at baseline.

Any additional analyses of secondary efficacy outcomes and biomarkers will be specified in the Study SAP.

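### The supportive MMRM adjusts for site but not for tau, the other randomisation stratum, so its overall-population standard error may be somewhat too large

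*Protocol*

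**What the plan says.** Section 6.3 of the protocol states that "participant randomization will be stratified by investigative site and tau pathology (low-medium versus high").

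Section 9.4.3 names the fixed effects of the MMRM for iADRS: "baseline score, pooled investigator, treatment, visit, treatment-by-visit interaction, baseline-by-visit interaction, concomitant AChEI and/or memantine use at baseline (yes/no), and age at baseline". The treatment contrast at Week 76, its p-value and its confidence interval are taken from that model. The same section says that the NCS, DPM and "MMRM models on iADRS will be assessed in the intermediate tau population and overall population". Section 9.4.4 carries the approach to ADAS-Cog13, ADCS-iADL, CDR-SB and MMSE, each to be "assessed using NCS with 2 DF, DPM, and MMRM analyses for the intermediate tau population and overall population".

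Two statements bear on how final the list is. For the primary NCS model, Section 9.4.3 leaves the covariates open: "potentially other covariates will be included in the model and specified in the Study SAP". The MMRM list has no such clause. More generally, Section 9.4.3 refers to the SAP for "Details about these analyses, as well as other sensitivity analyses including NCS with 3 degree of freedom", and Section 9.4.1 says that "a more technical and detailed description of the statistical analyses will be described in the SAPs".

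**The concern.** One of the two stratification factors enters the MMRM and the other does not, and no reason is given. In the low-medium tau population this is harmless, because the stratum is constant there. In the overall population about one-third of participants are expected to have high tau, and the two groups may decline at different rates.

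If they do, a model without tau counts the between-stratum difference as residual noise. Randomisation within tau strata has already balanced that difference across the arms, so most of it does not contribute to the actual sampling variation of the treatment contrast. The model then reports a larger standard error than it should. At stake are a little precision and power in a supportive analysis of iADRS and of four secondary scales. The treatment estimate stays unbiased and the false-positive rate does not rise.

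**Working it through.** **Inputs from the protocol (Sections 6.3 and 9.2).** 1800 randomised 1:1; one-third high tau; 30% discontinuation; SD 11.06; placebo and donanemab declines of 10.06 and 6.86, a difference of 3.20 points.

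**Assumptions.** D is the high-minus-low tau difference in 76-week decline. The protocol does not give it, so 3, 5 and 8 points are used. The SD comes from a study in intermediate tau (Section 2.2.2) and is applied to both strata. Arms are exactly balanced within tau at randomisation, and dropout is random. A single-visit ANCOVA at Week 76 stands in for the MMRM; the MMRM also uses dropouts' earlier visits, so the results are approximate.

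**The protocol's own figure.** About 1000 randomised in low-medium tau gives 500 × 0.70 = 350 completers per arm. SE = 11.06 × √(2/350) = 0.836, and power = Φ(3.20/0.836 − 1.96) = 96.9%. This agrees with the stated power above 95%.

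**Overall population, case A: baseline score absorbs none of D.** Completers n = 1800 × 0.70 = 1260; v = 11.06² = 122.32.

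- SE with tau: √(4v/n) = 0.623.
- Reported SE without tau: √(4(v + (2/9)D²)/n), where 2/9 = (1/3)(2/3) is the variance of the stratum indicator.
- True SE without tau: √(4(v + 0.3 × (2/9)D²)/n). The factor 0.3 is the imbalance in tau that 30% random dropout brings back.
- Two-sided type I error: 2(1 − Φ(1.96 × reported/true)).

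| D | Reported SE without tau | Excess over 0.623 | True SE | Reported/true | Type I error | Power at 2.0 points (with tau 89.4%) |
|---|---|---|---|---|---|---|
| 3 | 0.628 | +0.8% | 0.625 | 1.006 | 4.9% | 89.1% |
| 5 | 0.637 | +2.2% | 0.627 | 1.016 | 4.7% | 88.4% |
| 8 | 0.658 | +5.7% | 0.634 | 1.039 | 4.2% | 86.9% |

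The 2.0-point effect is also an assumption. At the protocol's 3.2 points and D = 8, power is 99.87% without tau and about 99.92% with it.

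**Case B: baseline score absorbs part of D.** Assumed: high-tau baseline 6 points lower, baseline SD 14, within-stratum correlation of baseline with change 0.3.

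- With tau, residual variance = 122.32 × (1 − 0.3²) = 111.31 and SE = 0.594.
- Without tau, residual variance = v + (2/9)D² − [0.3 × 14 × 11.06 + (2/9) × 6 × D]² / [14² + (2/9) × 6²]. This is 111.85, 114.05 or 120.55 for D = 3, 5 or 8.
- The SE excess is +0.2%, +1.2% or +4.1%, and type I error is 5.0%, 4.8% or 4.4%.
- Power at 2.0 points falls by 0.1, 0.4 or 1.5 percentage points.

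Simulation of both cases, 80,000 trials per setting, agrees with these values.

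**Sensitivity.**

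- If the high-tau SD is 14 instead, within-stratum variance in case A becomes (2/3) × 122.32 + (1/3) × 196 = 146.88, and the excess is +0.7%, +1.9% or +4.7%. With SD 16 it is +0.6%, +1.6% or +4.2%.
- If tau were also exactly balanced among completers, the true SE would stay at 0.623 and type I error at D = 8 would be 3.8%.
- Site count and block size are not given. Incomplete blocks would move type I error back towards 5%.

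**Other scales.** The protocol gives no SD or stratum difference for them. In scale-free form the excess is √(1 + (2/9)d²) − 1: +0.7%, +2.7% or +6.1% for a stratum difference of d = 0.25, 0.5 or 0.75 within-stratum SD.

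**The case against.** The strongest reply is that this belongs to the SAP, which was not available for this review. Section 9.4.1 calls the protocol text a summary, Section 9.4.3 leaves details of these very analyses to the SAP, and a list of terms that will be included does not say that nothing else may be. No statement in the protocol requires every stratification factor to enter every model. The analysis is supportive, the error is in the conservative direction, and its size depends on a stratum difference that the protocol does not give. The largest value used, 8 points, is about 80% of the whole assumed placebo decline (8/10.06). Age, symptomatic medication and pooled investigator might absorb some of the difference too.

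Most of this stands, and it sets the weight of the point. The SAP may already include tau, and repairing the list there is enough. The reply does not remove the point, because the protocol is not silent: it gives a specific list, carries one stratum into it and leaves the other out, and takes the p-value and interval from that model. The open-covariate clause is attached to the NCS model only. Under Section 9.4.1, a change to a described method that alters no principal feature must be described and justified in the SAP and the clinical study report, so an addition of tau is best made explicit.

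**Conclusion.** The point holds, at low weight. As listed, the overall-population MMRM omits a known stratification factor. For assumed stratum differences of 3 to 8 iADRS points, its standard error would be 0.8% to 5.7% larger than necessary if baseline score absorbs nothing, and 0.2% to 4.1% larger in the partial-absorption case. Actual two-sided type I error would lie between 4.2% and 5.0% under random dropout. Power loss is 0.1 to 2.6 percentage points at an assumed 2.0-point effect and immaterial at 3.2 points. The excess is nil if the strata decline equally given baseline. These figures rest on the assumed D, a common SD except where varied, balance within tau at randomisation, and a single-visit approximation. The primary NCS analysis and everything in the low-medium tau population are untouched.

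**What to change.** For the overall population, add tau stratum (low-medium versus high) and tau-by-visit to the MMRM for iADRS, ADAS-Cog13, ADCS-iADL, CDR-SB and MMSE. The interaction is needed because a difference in rate of decline grows over time, and a main effect alone may recover only part of the precision at Week 76. The change can be made in the list in Section 9.4.3 or in the SAP. It costs one line of text and a few model degrees of freedom among about 1800 participants. Tau stratum is already recorded for randomisation.

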9.4.4. Secondary Endpoint(s)

Similar to the primary endpoint of iADRS, each of the secondary efficacy outcomes will be assessed using NCS with 2 DF, DPM, and MMRM analyses for the intermediate tau population and overall population. These secondary efficacy outcomes include ADAS-Cog₁₃, ADCS-iADL, CDR-SB, and MMSE.

Longitudinal changes from baseline in amyloid plaque (as measured by florbetapir F18 PET scan) will be analyzed using MMRM including the following terms in the model: baseline biomarker value, treatment, visit, treatment-by-visit interaction, and baseline-by-visit interaction.

The change from baseline to endpoint in tau deposition (as measured by flortaucipir PET scan) will be analyzed using an analysis of covariance (ANCOVA) model with terms of baseline value and treatment. Atrophy in vMRI parameters will be analyzed using MMRM including the following terms in the model: treatment, visit, treatment-by-visit interaction, baseline vMRI, intracranial volume, and age at baseline.

Any additional analyses of secondary efficacy outcomes and biomarkers will be specified in the Study SAP.

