Tolerance Interval for Visit (Days)	0	-7 to +10	±7	±7	±7	±7	±7	±7	±7	±7	±7	±7	±7	
MRI		X		X			X							Perform at least 1 day prior to or after cognitive and functional tests, if applicable. MRI at V3 is to be performed and reviewed prior to V3 infusion and may occur no sooner than 21 days after the first infusion. If infusions are suspended after the first, second, or third dose, an MRI is to be performed and reviewed prior to the fourth infusion. MRI at V5 is to be performed and reviewed prior to V5 infusion. MRI at V5 may occur up to 14 days before the scheduled visit window without protocol deviation. Unscheduled MRIs may be performed at the discretion of investigator, for example if titration is delayed due to temporary suspension of infusions.
Additional Efficacy Measures														
Florbetapir F18 PET scan							X							

Visits 15 through 21 and EDa

Visits without cognitive and functional scales are eligible to be conducted remotely, via mobile healthcare coordinated with and approved by the sponsor, if permitted by local regulations.

Visit No.:	15	16	17	18	19	20	21	EDa	Notes
End of Week Relative to Study Medication Start	52	56	60	64	68	72	76		If a participant discontinues before V21, perform EDa assessments, then the follow-up visits 12 weeks after the last dose received.
Tolerance Interval for Visit (Days)	±7	±7	±7	±7	±7	±7	±7		
Contact IWRS – register visit	X	X	X	X	X	X	X	X	For all visits.
Contact IWRS – dispensation of IP	X	X	X	X	X	X			For visits where IP will be dispensed.
Physical/neurological examination	X			X			X	X	V18 is a brief physical and neurological exam, as described in Section 8.2.1. Any clinically significant changes from baseline on physical/neurological examinations should be noted on the AE CRF.
Previous/concomitant medications	X	X	X	X	X	X	X	X	
Preexisting conditions/adverse events	X	X	X	X	X	X	X	X	
IP administered	X	X	X	X	X	X			Administered by IV infusion. The participant should be observed for a minimum of 60 minutes following the end of each infusion.
Efficacy Measures									
ADAS-Cog ₁₃	X			X			X	X	See footnote a.
ADCS-ADL	X			X			X	X	See footnote a.
CDR	X			X			X	X	See footnote a.
MMSE	X			X			X	X	See footnote a.
DSST medicines version	X			X			X	X	Collect via eCOA only when available.
Safety Assessment									
C-SSRS since last visit	X	X	X	X	X	X	X	X	If visit is not conducted on site, may collect by phone.

Visit No.:	15	16	17	18	19	20	21	EDa	Notes

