2.3. Benefit/Risk Assessment

More detailed information about the known and expected benefits and risks and reasonably expected adverse events (AEs) of donanemab can be found in the IB.

3. Objectives and Endpoints

Objectives	Endpoints
Primary	
To assess the effect of donanemab versus placebo on clinical progression in participants with early symptomatic AD	iADRS change from baseline through Week 76 in at least one of 
 • the low-medium tau pathology population or • the overall population
Secondary	
To assess the effect of donanemab versus placebo on clinical progression in participants with early symptomatic AD	Change from baseline through Week 76 in at least one of 
 • the low-medium tau pathology population or • the overall population as measured by: 
 • CDR-SB • ADAS-Cog₁₃ score • ADCS-iADL score • MMSE score
To assess the effect of donanemab versus placebo on brain amyloid deposition	Change in brain amyloid plaque deposition from baseline through Week 76 as measured by florbetapir F18 PET scan
To assess the effect of donanemab versus placebo on brain tau deposition	Change in brain tau deposition from baseline through Week 76 as measured by flortaucipir F18 PET scan
To assess the effect of donanemab versus placebo on brain region volumes	Change in volumetric MRI measures from baseline through Week 76
To evaluate safety and tolerability of donanemab	Standard safety assessments: 
 • Spontaneously reported AEs • Clinical laboratory tests • Vital sign and body weight measurements • 12-lead ECGs

Objectives	Endpoints
	
 • Physical and neurological examinations MRI (ARIA and emergent radiological findings) Infusion related reactions C-SSRS
To assess peripheral PK and presence of anti-donanemab antibodies	Plasma PK of donanemab ADAs against donanemab including 
 • treatment-emergent ADAs • neutralizing antibodies
Tertiary/Exploratory	
To assess the effect of donanemab versus placebo on blood-based biomarkers	Plasma 
 • NfL • GFAP • P-tau • Aβ levels
To assess the effect of donanemab versus placebo on cognition	Change in DSST - Medicines Version from baseline through Week 76.
To assess the efficacy of donanemab to prolong time in the current disease state	CDR global score CDR-SB
Extension Period	

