8.1.2.5. Biomarker Efficacy Measures

Florbetapir F18 PET scan

Change in amyloid burden (as assessed by florbetapir F18 PET) will be compared in donanemab- and placebo-treated participants.

Flortaucipir F18 PET scan

Change in tau pathology (as assessed by flortaucipir F18 PET) will be compared in donanemab- and placebo-treated participants.

Volumetric MRI

Volumetric magnetic resonance imaging (vMRI) of the brain will be performed according to the SoA (Section 1.3). Donanemab- and placebo-treatment effects on vMRI will be assessed and compared to evaluate the loss of brain volume that occurs in AD participants.

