9.1. Statistical Hypotheses

The primary efficacy objective will be assessed using a Natural Cubic Spline (NCS) model with 2 degrees of freedom of the primary outcome iADRS at Month 18.

The primary efficacy analysis will be conducted on two populations: the intermediate tau population at baseline and the overall population. The hypothesis will be tested with a control of family wise 2-sided type I error rate of 5% following the chain procedure (Millen and Dmitrienko 2011).

The testing scheme, and a graphic testing procedure that will be used to control the overall false positive rate for the primary endpoint and major secondary endpoints will be described in the Study SAP.

Major secondary hypotheses defined in a similar manner are that donanemab is superior to placebo with regard to:

- Clinical progression in participants with early symptomatic AD through Week 76, as measured by MMSE, ADAS-Cog₁₃, CDR-SB, and ADCS-iADL
- Brain amyloid deposition at Week 76 measured by florbetapir F18 PET scan
- Brain tau deposition at Week 76 measured by flortaucipir F18 PET scan
- Brain region volumes at Week 76 measured by vMRI

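### The volumetric MRI model in Section 9.4.4 has no baseline-by-visit term, unlike the amyloid and iADRS MMRMs, and may lose some precision at Week 76

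*Protocol*

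**What the plan says.** Section 9.4.4 fixes the fixed effects of the vMRI MMRM as "treatment, visit, treatment-by-visit interaction, baseline vMRI, intracranial volume, and age at baseline". Baseline volume, intracranial volume and age are all main effects, and only treatment interacts with visit.

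The two sibling models differ. The amyloid PET MMRM, in the same section, has "baseline biomarker value, treatment, visit, treatment-by-visit interaction, and baseline-by-visit interaction". The iADRS MMRM in Section 9.4.3 starts with "baseline score, pooled investigator, treatment, visit, treatment-by-visit interaction, baseline-by-visit interaction" and goes on to symptomatic medication use and age as main effects. No reason is given for leaving baseline-by-visit out of the vMRI model alone.

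The endpoint in the Section 3 table is "Change in volumetric MRI measures from baseline through Week 76". Section 9.1 names the major secondary hypothesis as "Brain region volumes at Week 76 measured by vMRI". Section 8.1.2.5 says that vMRI follows the Schedule of Activities, whose MRI row for the double-blind period is marked at Weeks 4, 12, 24, 52 and 76. The protocol does not say which of these scans enter the vMRI model, what covariance structure it uses, or what variance or baseline relation is expected.

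**The concern.** Atrophy as a change from baseline is close to zero at Week 4 and largest at Week 76. If baseline volume predicts how fast a participant loses volume, its effect on the change is small early and large late. A single coefficient has to serve every visit. In a GLS fit it is an inverse-covariance weighted average of the visit-specific effects, and the early visits have the smaller variances. The value applied at Week 76 can then fall well below the effect that holds at Week 76.

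At stake is the precision of a listed major secondary comparison, and how fully chance imbalance in baseline volume is corrected at the time point that is tested.

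**Working it through.** The protocol states no power or variance for vMRI, so there is no plan figure to reproduce. Its only power statement (Section 9.2) concerns iADRS and does not bear on this point.

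**Inputs from the protocol:** the model terms (9.4.4), the Week 76 time point (9.1) and MRI at Weeks 4, 12, 24, 52 and 76 (Schedule of Activities).

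**Assumptions, none of them from the protocol:** true 76-week atrophy has SD 1 and accrues linearly. Baseline volume X is standardised and correlates ρ with it. Scan error has SD k at each visit, and the baseline scan's error is shared by all changes and unrelated to X. All five visits are used with an unstructured covariance and complete data.

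**Formulas.** With t in weeks:
- Baseline effect at visit t: β_t = ρ·t/76.
- Residual covariance given X: V_st = (1−ρ²)(s/76)(t/76) + k² + k²·[s = t].
- Common coefficient: b = (1′S⁻¹β)/(1′S⁻¹1), with S = V + (β−b)(β−b)′, solved iteratively.
- Week 76 variance ratio, without versus with the interaction: 1 + (ρ−b)²/V₇₆, where V₇₆ = 1−ρ²+2k².

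**Results, five visits:**

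| ρ | k | b | V₇₆ | (ρ−b)² | variance ratio | SE increase |
|---|---|---|---|---|---|---|
| 0.3 | 0.2 | 0.009 | 0.99 | 0.0848 | 1.086 | 4.2% |
| 0.3 | 0.5 | 0.041 | 1.41 | 0.0672 | 1.048 | 2.4% |
| 0.5 | 0.2 | 0.018 | 0.83 | 0.2327 | 1.280 | 13.2% |
| 0.5 | 0.5 | 0.077 | 1.25 | 0.1786 | 1.143 | 6.9% |

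At ρ = 0.3 and k = 0.2 the weights on Weeks 4, 12, 24, 52 and 76 are 0.46, 0.39, 0.28, 0.04 and −0.17, so the early scans dominate. Over the four rows b is 3% to 15% of the Week 76 effect.

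**How far this depends on the assumptions:**

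| Change | b as share of Week 76 effect | SE increase, ρ = 0.3 | SE increase, ρ = 0.5 |
|---|---|---|---|
| k = 1, five visits | 28-30% | 0.8% | 2.2% |
| Weeks 24, 52, 76 only; k = 0.2-0.5 | 11-39% | 1.3-3.6% | 3.6-11.0% |
| Weeks 52, 76 only; k = 0.2-0.5 | 39-73% | 0.3-1.7% | 0.7-4.7% |
| Half the baseline effect constant over time, β_t = ρ(0.5 + 0.5·t/76); five visits; k = 0.2-0.5 | 51-58% | 0.6-1.1% | 1.8-3.4% |

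**Simulation check.** A separate simulation had 700 complete cases, 600 replicates per scenario, no treatment effect and noise of 0.25 to 1 relative to a random-slope SD of 1. Without the interaction, the fitted coefficient was 4% to 27% of the Week 76 effect; with it, the ratio was 0.99 to 1.01. The mean Week 76 contrast was within 0.01 of zero under both models. Rejection rates at the nominal 5% level were 5.0-6.3% without the term and 4.7-6.8% with it.

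**The case against.** **The inputs are not in the protocol.** Noise, correlation and the shape of the baseline effect are all assumed. This stands. A reader might infer that the Week 76 contrast is left almost unadjusted, but that is one corner of the range: low noise, all five scans and a baseline effect strictly proportional to time.

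**The early scans may be there for safety only.** The MRI row sits among the safety measures, and the schedule says "MRI at V3 is to be performed and reviewed prior to V3 infusion". If Weeks 4 and 12 do not enter the vMRI model, the pull to early visits weakens. Section 8.1.2.5 ties vMRI to that same schedule, so five visits remains a fair reading, though not a settled one.

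**The covariance structure is not stated.** Under compound symmetry with complete data the weights are equal, and the common coefficient is (4+12+24+52+76)/5/76 = 33.6/76 = 44% of the Week 76 value. This also stands.

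**Models differ by endpoint throughout Section 9, which calls itself a summary.** True, so the inconsistency alone proves little. But the protocol does list this model's terms, and its closing deferral in 9.4.4 covers additional analyses.

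**Two further readings go too far.** One is that age-by-visit and intracranial volume-by-visit are also needed to match the sibling models. Neither sibling has them: the iADRS MMRM has age as a main effect only, the amyloid MMRM has no age term, and neither uses intracranial volume. The other is that the estimate is biased. With complete data it is not. Bias could arise if dropout depended on baseline volume differently by arm, but the protocol gives no such pattern, and Section 7.1 keeps participants who stop treatment in the study.

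**Conclusion.** The omission is real, and it sets the vMRI model apart from the two other MMRMs for an endpoint listed among the major secondary hypotheses. If the baseline effect grows with time and the scans from Week 4 onward all enter the model, the single coefficient leans on the early visits and may under-adjust the Week 76 contrast.

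Under the first set of assumptions above, the Week 76 standard error is about 2-4% larger at a correlation of 0.3 and 7-13% larger at 0.5. It is smaller in each alternative case examined. The cost is mainly precision; the documents do not support a claim of bias or of inflated type I error. This is a minor point, and a free improvement.

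**What to change.** In Section 9.4.4, add baseline vMRI-by-visit to the terms of the vMRI MMRM, as the amyloid and iADRS MMRMs already do for their baselines, or state why it is left out. This costs one phrase of model wording and a few degrees of freedom: four extra parameters if all five visits are used. It needs no new data.
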